9.1. Appendix 1: Time & Events

9.1.1. Protocol Defined Time & Events

Table 1 Time and Events – Pilot Phase

Procedures	Clinic Visit	Home Monitoring (~ 3 days)	Telephone Contact ^a (TC)	Repeat Clinic Visit ^b	Home Monitoring ^b (~ 3 days)	Telephone Contact ^{a,b}	EWD
	Screening Day 0						
Informed consent	X						
Eligibility criteria	X						
Demography	X						
Medical and ALS history	X						
Brief neurological exam	X			X			
AEs/SAEs	X		X	X		X	X
Sensor placement	X	X		X	X		
Reference tasks	X			X			
Subject completes diary		X			X		
Site obtains diary information			X			X	X
Device impact questionnaire			X			X	X

- a. Telephone contact to follow the 3-day home monitoring period to ensure the subject has completed the home monitoring period, diary, and to assess AEs, as appropriate. The expectation is that this call would occur on the first weekday following the home monitoring period.
- b. May be repeated as necessary

Table 2 Time and Events – Core Study Phase

Study Day/Week ^a	Screen/Baseline Day 1/Week 0	Weeks 0, 4, 8	Week 12	Weeks 12, 16, 20	Week 24	Weeks 24, 28, 32	Week 36	Weeks 36, 40, 44, 48 ^c	Week 48 or EWD
	Clinic Visit 1 ^b	Home Monitoring (~3 days)	Clinic Visit 2	Home Monitoring (~3 days)	Clinic Visit 3	Home Monitoring (~3 days)	Clinic Visit 4	Home Monitoring (~3 days)	Clinic Visit 5
Procedures									
Informed consent	X ^d								
Eligibility criteria	X ^d								
Demography	X ^d								
Medical and ALS history	X ^d								
Neurological exam	X								
Smoking details	X		X		X		X		X
Brief neurological exam			X		X		X		X
AEs/SAEs ^e	X	X	X	X	X	X	X	X	X
Concomitant medications ^e	X	X	X	X	X	X	X	X	X
ALSFRS-R ^e	X	X	X	X	X	X	X	X	X
FVC	X		X		X		X		X
Speech assessment	X		X		X		X		X
Sensor placement	X	X	X	X	X	X	X	X	X
Reference tasks	X		X		X		X		X
Device impact questionnaire			X		X		X		X
Subject completes diary		X		X		X		X	
Site obtains diary information ^f		X	X	X	X	X	X	X	X
Follow-up Telephone Contact ^g		X		X		X		X	

- a. Clinic visits and home monitoring periods should be conducted within ± 7 days of the scheduled visit/home period and should be scheduled according to the Baseline Visit.
- b. Subjects transitioning from the Pilot Phase do not need to perform these procedures.
- c. The Week 48 home monitoring period will occur the three days prior to the Week 48 in-clinic visit (Visit 5).
- d. Assessed in clinic at Weeks 0, 12, 24, 36, and 48 and by telephone at Weeks 0, 4, 8, 12, 16, 20, 24, 28, 32, 36, 40, and 44.

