9.3.2. Baseline Definition & Derivations

9.3.2.1. Baseline Definitions

For all endpoints the baseline value will be the latest assessment prior to or at the baseline visit (Visitnum=10 or 90), with the following exceptions which may use the TC at week 0 (Visitnum=100) if available:

- Actigraphy endpoints
- HRV endpoints
- Speech endpoints
- ALSFRS-R
- FVC

For all endpoints this will be referred to as Baseline, Week 0.

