9.4. Appendix 4: Derived and Transformed Data

9.4.1. General

Multiple Measurements at One Time Point

 For the ALSFRS-R, if the closest assessment is not evaluable, the other assessment would be used.
Study Day

 Calculated as the number of days from baseline visit (visitnum=10 or 90) 
 Ref Date = Missing → Study Day = Missing Ref Date < Baseline Visit Date → Study Day = Ref Date – Baseline Visit Date Ref Date ≥ Baseline Visit Date → Study Day = Ref Date – Baseline Visit Date + 1

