9.4.3. Exploratory

ALSFRS-R Total Score

The ALS functional rating scale – revised (ALSFRS-R) assesses the functioning of ALS subjects across 4 domains: gross motor activity, fine motor activity, bulbar and respiratory function. The ALSFRS-R [Cedarbaum, 1999] consists of 12 questions each of which are scored on a 5-point scale from 0-4, where 4 is the best possible outcome and 0 is the worst.
 
The total score will be calculated by summing responses to each of the 12 individual questions. The maximum total score is therefore 48, lower scores indicate worse functioning. If there are any missing questions, then the total score will be set to missing.
 
ALSFRS will be grouped to four different domains: Fine motor, Gross motor, Respiratory and Bulbar Domain [Cedarbaum, 1999]

FVC

FVC is a measure of respiratory function and is the volume of air that can forcibly be blown out after a single, full breath. FVC is a sensitive measure of ALS disease progression, is used as a standard test for ALS management, and is recommended as a secondary outcome measure in ALS clinical trials [Cudkowicz, 2004; Czaplinski, 2006; Clavelou, 2013].
 
FVC will be performed by experienced site personnel according to local protocol using a calibrated spirometer. Every effort should be made to have the same individual perform the FVC for a given subject throughout the study. For each time point, the best FVC result (in litres) will be recorded in the eCRF.

Relative Rate of Decline and Monthly Rate of Decline (Slope)

Relative Rate of Decline = $\frac{\text{Value at a time point} - \text{Value at the Baseline}}{\text{Value at the Baseline}}$
 
 $\frac{\text{Monthly rate of decline at each visit} = \frac{\text{Change from baseline of the endpoint at each post-baseline visit}}{\text{Study day}/30.4}}$ 
 
Monthly Rate of Decline= Average of Monthly Rate of Decline at each visit and is populated only for the last visit.
 
For Monthly Rate of Decline, if an assessment took place over a number of consecutive days then the average of that will be taken and the recent visit (last time point) will be considered to calculate study day.

Actigraphy

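### The monthly rate of decline divides by a study day that exceeds the time between the two measurements, so absolute rates come out modestly too small, most for early visits and early leavers

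*SAP*

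**What the plan says.** Four rules in the SAP combine here.

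- **Numerator (Section 9.4.3).** The monthly rate at each visit uses "Change from baseline of the endpoint at each post-baseline visit", divided by study day/30.4. The subject's monthly rate is the unweighted average of these visit rates, stored at the last visit.
- **Multi-day assessments (Section 9.4.3).** If an assessment ran over consecutive days, its values are averaged, and "the recent visit (last time point) will be considered to calculate study day".
- **Study day (Section 9.4.1).** It is "Calculated as the number of days from baseline visit (visitnum=10 or 90"), and on or after that visit "Study Day = Ref Date – Baseline Visit Date + 1".
- **Baseline value (Section 9.3.2.1).** The default is the latest assessment up to the baseline visit, "with the following exceptions which may use the TC at week 0 (Visitnum=100) if available". The exceptions are actigraphy, HRV, speech, ALSFRS-R and FVC.

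Section 2.3 places roughly 3 days of home wear after the clinic visits. Footnote a of the Core Phase schedule (Section 9.1.1) adds: "Clinic visits and home monitoring periods should be conducted within ± 7 days of the scheduled visit/home period".

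**The concern.** A rate per month needs the time over which the change took place. The numerator here runs from the baseline recording to the later recording. The divisor runs from the clinic visit to the last day of the later recording, plus 1. It differs from the elapsed time in three ways:

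1. The added day is a labelling convention (no day 0), not elapsed time.
2. When the Week 0 home recording supplies the baseline value, the clock has already been running since the clinic visit.
3. The later value is a mean over several days, so it belongs to the middle of the recording but is dated at its end.

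When the Week 0 recording follows the visit, as Section 2.3 describes, all three lengthen the divisor and shrink the absolute rate. For endpoints that rise with progression, such as time lying, it is the rise that is understated. The excess is a fixed few days, so it matters most when follow-up is short. It therefore differs between early leavers and completers, and between device endpoints and single-day assessments.

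**Working it through.** The SAP gives no numerical rate to reproduce, so the check applies its formulas to its own schedule.

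**Inputs.** Post-baseline home recordings at Weeks 4, 8, …, 48, with the Week 48 recording in the three days before that clinic visit (Section 9.1.1). The recording length is given only as about 3 days, so 3 days is assumed, starting either on the clinic-visit day (A) or the day after (B). The Week 0 recording is taken as baseline, and decline is assumed linear.

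**Formula.** Planned rate / true rate = elapsed days / study day, where elapsed days = midpoint of the later recording minus midpoint of the Week 0 recording.

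**Week 4, case A** (clinic visit = day 0). The Week 0 recording covers days 0–2, midpoint 1. The Week 4 recording covers days 28–30, midpoint 29. Elapsed = 29 − 1 = 28. Study day = 30 − 0 + 1 = 31. The 3 excess days are 1 (clock origin) + 1 (last-day dating) + 1 (added day). In case B the origin accounts for 2, so the excess is 4.

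| Visit | A: elapsed/study day | Ratio | B: elapsed/study day | Ratio |
|---|---|---|---|---|
| Week 4 | 28/31 | 0.903 | 28/32 | 0.875 |
| Week 8 | 56/59 | 0.949 | 56/60 | 0.933 |
| Week 12 | 84/87 | 0.966 | 84/88 | 0.955 |
| Week 24 | 168/171 | 0.982 | 168/172 | 0.977 |
| Week 48 | 333/336 | 0.991 | 332/336 | 0.988 |
| Mean, Weeks 4–12 | | 0.939 | | 0.921 |
| Mean, all 12 visits | | 0.974 | | 0.965 |

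The reported average is thus low by 2.6% (A) or 3.5% (B) with all 12 visits, and by 6.1% or 7.9% with data only through Week 12.

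**Device endpoint with the clinic visit as baseline.** Only last-day dating and the added day remain. In case A at Week 4 this is 29/31 = 0.935, or 6.5% low.

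**Single-day assessment with a clinic-visit baseline.** Only the added day remains: 28/29 = 0.966 at Week 4 and a mean of 0.991 over 12 four-weekly visits. For FVC and speech (Weeks 12, 24, 36, 48) the ratios are 84/85, 168/169, 252/253 and 336/337, mean 0.994.

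**Extreme case.** If the Week 0 recording starts 7 days late and every later recording is on schedule, Week 4 gives 21/31 = 0.677 and the mean over 12 visits is 0.912.

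**Slope correlations.** A scale factor common to all subjects leaves a correlation unchanged. If the factor varies independently of the slope, with coefficient of variation k, and the slope has coefficient of variation c, the correlation is multiplied by 1/√(1 + k² + k²/c²). Let the factor be uniform between 0.912 and 0.974 for one endpoint only: mean 0.943, SD 0.062/√12 = 0.0179, k = 0.019, k² = 0.00036. With c = 0.3 (assumed) the multiplier is 1/√1.00436 = 0.998; with c = 0.8 it is 1/√1.00092 = 0.9995. An assumed correlation of 0.60 falls by about 0.001 or less.

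**The case against.** The strongest reply is that the reported figure barely moves. The Week 4 rate is only one term in the average, and for a completer on schedule that average is off by about 3%. The added day is a common convention, and Section 7.1.1 tolerates up to 21 days between ALSFRS and actigraphy. The size argument stands for completers and limits the point. The tolerance argument does not: it decides which records may be paired, and does not justify a one-directional error in a divisor.

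It is also fair that Section 9.3.2.1 only permits the Week 0 baseline when available; otherwise the origin component disappears. The contrast between device endpoints and ALSFRS-R narrows as well if the ALSFRS-R baseline is taken from the Week 0 call.

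Three stronger readings are tempting, and the documents do not support them.

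- **A Pilot-phase clock.** A reader might infer from the two visit numbers in Section 9.4.1 that visit 10 is a Pilot visit, so that study day could include the whole Pilot Phase. Nothing says so. Sections 9.3.2.1 and 9.4.1 treat both numbers as the baseline visit, and the schedules give the Pilot visit as Screening Day 0 and the Core visit as Screen/Baseline.
- **The 7-day delay as typical.** The window allows it, but it delays only the baseline recording, whereas Section 2.3 describes wear following the clinic visit.
- **Materially distorted correlations.** The calculation above points to a negligible effect for subjects with all visits. The correlation models in Section 7.1.2 use absolute values and change from baseline, which have no study-day divisor. Slopes enter only through Appendix 11 displays such as Tables 2.67, 2.104 and 2.139.

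**Conclusion.** The derivation is wrong as written: numerator and divisor cover different intervals, and no section corrects this. Under linear decline, 3-day recordings and a Week 0 recording starting on the visit day or the day after, the error is about 10% to 12.5% at Week 4. In the reported average it is roughly 3% for completers and 6% to 8% for subjects followed only to Week 12. The late-baseline extreme gives about 9% on average. Single-day endpoints with a clinic-visit baseline lose under 1% on average.

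The consequence is a modest downward bias in the monthly-rate tables (for example 2.13 for time active), unequal across subjects and endpoints. The effect on slope-against-slope correlations is likely small; it has not been worked out for a mix of completers and early leavers. This is a derivation error worth correcting, not a threat to the study's main correlation analyses.

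**What to change.** In Section 9.4.3, replace study day/30.4 with: (mean date of the post-baseline recording or assessment − mean date of the recording or assessment used as that endpoint's baseline)/30.4, with no added day. Remove the sentence that dates a multi-day assessment at its last time point for this purpose. Study day as defined in Section 9.4.1 can stay for other uses.

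Under the assumptions above the ratio becomes 1.00 at every visit (28/28 at Week 4, 84/84 at Week 12). No separate rule on the clock's origin is needed, because each endpoint is dated from its own baseline assessment.

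The cost is a short wording change and one derivation line; the dates are already in the data. The monthly-rate tables and the slope displays would take the corrected value without further change.

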Actigraphy - Day/Night measures of physical activity - exploratory efficacy measures 2 measures for 24-hour recording period: Total Activity Score and Maximum Score														
Time Spent Active							Y							
Non-normalised (Average day time active and average night time active) & normalised (% daytime active; % night time active)				Y	Y		Y				Y	Y		
Over All Time Spent sedentary not lying							Y							
Non-normalised (Average day/night time spent sedentary not lying) & normalised (% daytime sedentary not lying; % night time sedentary not lying)				Y	Y		Y				Y	Y		
Over All Time Spent Lying							Y							
Non-normalised (Average day/night over all time spent lying) & normalised (% daytime lying; % night time lying)				Y	Y		Y				Y	Y		
Over All Time Spent Sedentary							Y							

Endpoint / Parameter/ Display Type	Absolute							Change from Baseline						
	Stats Analysis			Summary		Individual		Stats Analysis			Summary		Individual	
	T	F	L	T	F[1]	F	L	T	F	L	T	F[1]	F	L
Non-normalised (Average day/night over all time spent sedentary) & normalised (% daytime sedentary; % night time sedentary)				Y	Y		Y				Y	Y		
Total Activity Score Day/Night (Total Day time Activity score/hour; Total Night Time Activity score/hour)				Y	Y		Y				Y	Y		
Total Activity Score – 24 hour (derived by adding up the day & night scores)				Y	Y		Y				Y	Y		
Maximum Score –24 Hour (Maximum score of day OR night for each 24-hour recording) And Average of 3 values				Y	Y		Y				Y	Y		
Active Periods (Numbers) normalised / hr				Y	Y		Y							
Active Periods (Duration)				Y	Y		Y				Y	Y		
Relationship between the ALSFRS and actigraphy measures	Y	Y						Y	Y					
Actigraphy - Night Time Rest Endpoints - exploratory efficacy measures														
Number Night Time Movement Episodes/Hr (use average)				Y	Y		Y				Y	Y		
Percent Time Night- time Rest Efficiency (use average)				Y	Y		Y				Y	Y		
Rest Fragmentation Index (use average)				Y	Y		Y				Y	Y		
Average Duration Movement Episodes				Y	Y		Y				Y	Y		

Endpoint / Parameter/ Display Type	Absolute						Change from Baseline							
	Stats Analysis			Summary		Individual		Stats Analysis			Summary		Individual	
	T	F	L	T	F[1]	F	L	T	F	L	T	F[1]	F	L
Data Quality Deviators														
Data Quality Deviators for Actigraphy				Y										
Data Quality Deviators for Heart Rate Variability				Y										
Reconciliation for Actigraphy and Diary Data														
Reconciliation of Actigraphy and Diary Data				Y										

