- The absolute values and change from baseline in the time spent active (day only), Time Spent sedentary not lying (day only), Time Spent Lying (day only), Time Spent Sedentary (day only), Total Activity Score (By 24 Hour and by Day), Maximum Score (By 24 Hour and by Day), Active Periods (Numbers) (day only), Active Periods (Duration) (day only) will be analysed for correlation with the absolute values and change from

Statistical Analyses	

 ○ Heart Rate Variability 
 ▪ The absolute values and change from baseline in the heart rate variability endpoints will be analyzed for correlation with the absolute values and change from baseline in the Total score of ALSFRS-R, respectively. ▪ For the above endpoints analyzed for correlation, scatter plots will be done ○ Speech assessment 
 ▪ The absolute values and change from baseline in the speech endpoints will be analyzed for correlation with the absolute values and change from baseline in the Total ALSFRS-R, respectively. ▪ The absolute values and change from baseline in the speech endpoints will be analyzed for correlation with the absolute values and change from baseline of bulbar domain and respiratory domain of ALSFRS-R, respectively. ▪ The absolute values and change from baseline in the speech endpoints will be analyzed for correlation with the absolute values and change from baseline in the FVC, respectively. 	
baseline to the-gross motor domain and fine motor domain of ALSFRS-R, respectively.
 
For the above endpoints analyzed for correlation, scatter plots will be done
 
The correlation analysis will be performed on both non normalized and normalized data. Only the quality data (i.e. the data without the data quality deviators as defined in Section 7.1.1) will be used for the statistical analysis.
 
Only the quality data will be used for the statistical analysis.
 
Only the quality data will be used for the statistical analysis.

Model Results Presentation	

 ● Descriptive Statistics 
 ○ Data listings ○ Summary tables ○ Visualization graphs ● Correlation Analysis 
 ○ Result tables ○ Visualization graphs 	

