
Activity classifiers = Active / lying / “sedentary not lying”.
 
NMTMSG – expected to be 24 hr (1440 mins) but could be less if partial recording day NMTMSG = Active, lying, “sedentary not lying”, off
 
Each activity classifier & activity endpoint is recorded by McLaren TWICE, once for day time once for night time.
 
1440 = day time Active, day time lying, day time “sedentary not lying”, day time off + night time Active, night time lying, night time “sedentary not lying”, night time off
 
Therefore, wear time = 1440 minus [day off time + night off time]
 
Off time here represents the time that the sensor was either switched off or the patient was not wearing it (or both).
 
For all the parameters, derivation will be done twice – one with all data and one with the quality data (i.e., excluding data quality deviators).

For each endpoint for the CSR (& interpretation of the study) 3 splits of data will be reported:

- Day time activity endpoints – from McLaren
- Night time activity endpoints – from McLaren
- 24 hour endpoints – derived by GSK – add day time + night time values

DERIVED	Wear time (mins)	Time Active + Time sedentary [where time sedentary = time lying + time sedentary not lying]
DERIVED	Duration of day time wear time (mins)	Day time wear time = day time Active + day time lying + day time “sedentary not lying”
DERIVED	Duration of night time wear time (mins)	Night time wear time = night time Active + night time lying + night time “sedentary not lying”
ACTIVETM	Overall time spent active Average day time active % daytime ACTIVE % night time ACTIVE	Number mins per day/night for 24-hour recording period Add up the total amount of time active across all the recording periods and divide by the number of recording periods. 1 value per subject per time point DAYTIME ACTIVETM (Day 1+2+3) divided by total amount of day time duration across the 3 recording days – expressed as a % Where total amount of daytime duration = [Day 1-day time ACTIVETM + day time LIETM + day time “sedentary not lying” – SEDTMNL] + Day 2 (ditto) + Day 3 [ditto] NIGHTTIME ACTIVETM (Day

		
1+2+3) divide by total amount of night time duration across the 3 recording days – expressed as a %
 
Where total amount of night time duration = [Day 1-night time ACTIVETM + night time LIETM + night time “sedentary not lying” – SEDTMNL] + Day 2 (ditto) + Day 3 [ditto]

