SEDTMNL	
Overall time spent sedentary not lying
 
% daytime SEDENTARY NOT LYING
 
% night time SEDENTARY NOT LYING
	Needs the same approach as above
LIETM	
Overall time spent lying
 
% daytime LYING
 
% night time LYING
	Needs the same approach as above
SEDTM	
Over all time spent sedentary
 
% daytime SEDENTARY
 
% night time SEDENTARY
	Same Approach as above
OFFTM	Time spent with sensor	
ACTIVISC	
Total activity score
 
24- Hour
 
Daytime total activity score
 
Night time total activity score
	
Total Activity Score (add day + night)
 
Day time total activity score (Day 1+2+3) divide by the total day time for that protocol time point.
 
Night time total activity score Day (Day 1+2+3) divide by the total day time for that protocol time point.

MAXACTSC	The maximum score from a 1 min window in a 24-hour	3 values per protocol time point or more if more days are

	
period
 
Daytime maximum activity score
 
Daytime mean maximum activity score (mean of all recording periods)
 
Night time maximum activity score
 
Night time mean maximum activity score (mean of all recording)
	
recorded for home monitoring.
 
 • Take the maximum over the 3 days • Average over 3 days
WKPER01, WKPER02, WKPER05, WKPER15, WKPER30	Active Periods (Numbers)	To normalise 'Active Periods (Number)' to a per hour unit (Algorithm is given below)
WKPERDUR	Average duration of active periods greater than 1 minute.	

To normalise 'Active Periods (Number)' :

1. Add up the total number of 'active periods' for the recording periods (value 1).
 - Please note this is done by adding the 'number of active periods (all the categories) 1min<x<2min' + 'number of active periods 2min<x<5min' + 'number of active periods 5min<x<15min' + 'number of active periods 15min<x<30min' + 'number of active periods >30min'
2. Calculate the 'wear time' for the recording period in days(i.e. minutes/ 1440). (value 2).
 - Please remember that 'wear time = active + sedentary time' for the recording period (either day time or night time)
3. Value 1 / Value 2 is the normalised measure required

Rules for reconciliation of Actigraphy and Diary data

Actigraphy and Diary data will be reconciled and a frequency table on the rules below will be summarized;

Rule1: Subjects present both in Actigraphy and Diary data

Rule2: Subjects present only in Actigraphy data

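### The 24-hour Total Activity Score is a plain day-plus-night sum with no wear adjustment, and no rule covers the case where only one half passes its quality limit

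*SAP*

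**What the plan says.** Three places in the SAP define the 24-hour score as a sum.

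- Section 9.4.3, general rule for actigraphy: "24 hour endpoints – derived by GSK – add day time + night time values".
- Section 9.4.3, entry for the total activity score: "Total Activity Score (add day + night").
- Section 7.1.1, Table 3: "derived by adding up the day & night scores".

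None of them names a divisor, whether wear time or number of recording periods. The separate scores are treated differently. Table 3 lists them as "Total Day time Activity score/hour; Total Night Time Activity score/hour", and section 9.4.3 gives "Day time total activity score (Day 1+2+3) divide by the total day time for that protocol time point" for the day score. A recording period is "expected to be 24 hr (1440 mins) but could be less if partial recording day", so unequal recording lengths are foreseen.

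Section 7.1.1 sets actigraphy quality limits for day (under 9.1 h excluded) and for night (under 4.2 h excluded). It sets none for a 24-hour value; the only 24-hour completeness rule is for RMSSD. Section 7.1.2 puts "Total Activity Score (By 24 Hour and by Day") into the correlations with the gross and fine motor domains of ALSFRS-R, correlates the actigraphy endpoints with the ALSFRS-R total score as well, and restricts all of this to quality data. Section 9.11.4 plans quality-data tables for the 24-hour score.

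**The concern.** A sum of recorded scores is activity rate multiplied by hours worn. Two recordings from a patient whose activity has not changed give different 24-hour scores if the sensor was worn for different times. The SAP removes this dependence from the day and night scores but not from their total.

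The stake is the correlation with ALSFRS-R. If wear time changes as patients worsen, the sum changes with it, and part of the estimated correlation would describe wear and not activity. Section 7.1.1 itself allows that usable night data may be fewer because of disease or technology. Appendix 8 says conclusions will be drawn from the strength of the correlation coefficients, so an artefact in a coefficient goes straight into the conclusion.

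There is a second gap. If the day passes its limit and the night does not, the SAP does not say whether the 24-hour score is missing, equals the day score alone, or includes the failed night. "Quality data" is therefore not fully defined for this endpoint.

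**Working it through.** **Inputs from section 7.1.1.** Day 15 h and night 9 h (default sleep times 22:00 to 07:00); 2 h allowed for charging; limits of 70% by day and 60% by night; 22 h expected per 24-hour recording.

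**1. Reproduce the SAP's limits.**
- Day: 0.70 × (15 − 2) = 9.1 h.
- Night: 0.60 × (9 − 2) = 4.2 h.

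Both agree with the SAP.

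**2. Range of accepted wear if both halves must pass.** Minimum 9.1 + 4.2 = 13.3 h; expected full recording 22 h.

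**3. Effect on a sum of recorded scores.** Sum = day rate × day wear + night rate × night wear.
- Equal day and night rates: 22 / 13.3 = 1.65. The score at minimum wear is 1 − 13.3/22 = 39.5% lower than at 22 h, with no change in activity.
- Assumed rates of 100/h by day and 10/h by night (the SAP gives none). Minimum wear: 9.1 × 100 + 4.2 × 10 = 952.
  - Full recording of 13 + 9 h: 1300 + 90 = 1390; 1390 / 952 = 1.46.
  - Full recording of 15 + 7 h: 1500 + 70 = 1570; 1570 / 952 = 1.65.

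**4. One half missing.** Take a 13 + 9 h recording whose night data are dropped while the day score is kept as the total. The loss is 90 / 1390 = 6.5% at the assumed rates and 900 / 2200 = 40.9% at equal rates.

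**5. The other reading, hourly scores added.** Each half then has weight 0.50. By duration, night should have 9/24 = 0.375, so it counts 0.50 / 0.375 = 1.33 times too much. Assumed example: the day rate goes from 100 to 90 and the night rate from 10 to 22.
- Sum of rates: 110 to 112, a rise of 1.8%.
- Activity over 15 + 9 h: 1590 to 1548, a fall of 2.6%.

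**6. Check of two possible remedies at the assumed rates.**
- Pooled rate, (day score + night score) / (day wear + night wear). At 9.1 + 9 h: (910 + 90) / 18.1 = 55.2. At 15 + 4.2 h: (1500 + 42) / 19.2 = 80.3. It still moves with the mix of day and night wear.
- Fixed weights, 15 × day rate + 9 × night rate. In both cases 15 × 100 + 9 × 10 = 1590. It does not move.

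**The case against.** The strongest reply is that this is one exploratory endpoint among many, in a study with no primary endpoint, and that the SAP already contains safeguards. The day and night halves are screened separately, and every parameter is derived a second time without the deviators. The time-normalised day score is correlated alongside the 24-hour score. Wear times are tabulated by visit (Tables 2.1 to 2.6), so a drift in wear would be seen. These points stand, and they limit the damage. They do not correct the score: screening still leaves 13.3 h to 22 h, and a table of wear times adjusts nothing. Section 7.1.2 says that normalised and non-normalised data will both be analysed, but no normalised form of the 24-hour score is defined.

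Stronger readings are tempting, and the document does not support them.

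- *That the SAP adds two hourly rates.* It does not say so. The general rule adds day and night values, the hourly unit appears only on the day/night row of Table 3, and Listing 38 is a raw-data listing of the 24-hour score. Adding recorded scores is the natural reading; the hourly version is only an ambiguity.
- *That the range is 1.80-fold.* 24 / 13.3 = 1.80 needs 24 h of wear with no charging, and equal day and night rates. The SAP plans 22 h and says activity is not expected to be uniform.
- *That 24-hour data are unscreened.* They are screened by half; what is missing is the rule for combining the halves.

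**Conclusion.** The point holds as a defect in one derivation. As written, the 24-hour score depends on wear, and its treatment when only one half is valid is undefined. The possible difference from wear alone is up to about 1.65-fold at constant activity, or 1.46- to 1.65-fold at the assumed rates of 100/h and 10/h. It is reached only when both halves of one recording lie at their limits and the comparison recording is a full 22 h. It is a bound and says nothing about the usual size.

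A reader might infer that the correlation with ALSFRS-R will be spurious. The SAP gives no figures on how wear relates to disease stage, so that does not follow. If the loss is mainly at night and night activity is low, little of the sum is lost. The distortion arises only if wear changes with disease.

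**What to change.** Define the 24-hour Total Activity Score in section 9.4.3, and refer to that definition in Table 3, as

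15 × (day score / day wear hours) + 9 × (night score / night wear hours).

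Pool each half over the recording periods at the time point that pass its own limit (9.1 h by day, 4.2 h by night). Set the score to missing if the time point has no valid day data or no valid night data. The night term must be divided by night wear; section 9.4.3 now reads "Night time total activity score Day (Day 1+2+3) divide by the total day time for that protocol time point", which names day time as the divisor and should be corrected in the same edit.

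The formula assumes that the hourly rate while worn represents the unworn hours of the same half. Because each half is pooled separately, a recording period with one failed half still contributes its valid half.

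The cost is one changed derivation with its SAP wording, and the loss for this endpoint of time points that have only one valid half. No new data are needed.
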